	
 - Diabetes Treatment Satisfaction Questionnaire change (DTSQc), administered on Week 24 only - Hypoglycemia Fear Survey-II (HFS-II) - Diabetes Distress Scale (DDS) • HbA1c: change from baseline to Week 16 • FPG: change from baseline to Week 16 and Week 24 • Change in 7-point SMPG profiles, mean and per time-point from baseline to Week 16 and Week 24, • Insulin doses 
Patient care with the two approaches:
 
 • Study-specific resource requirements: Overall Study Experience-Sites (OSES) questionnaire part 1 (resource requirements) over the 24 week treatment period • Site-perceived patient relationship and satisfaction: OSES questionnaire part 2 at Week 24 • Patient interview in a subset of patients at Week 24 
Safety assessment managed by the two approaches:
 
 • Hypoglycemic events and incidence rate (as per the American Diabetes Association (ADA) classification) during the 24-week period in each group • Adverse events (including Injection site reactions and hypersensitivity), Serious AEs (SAEs) and Product Technical Complaints (PTCs)
ASSESSMENT SCHEDULE	See study flowchart in Section 1.2 .
STATISTICAL CONSIDERATIONS	
Sample size determination:
 
This is a pilot study, consequently no formal sample size calculation was done.
 
The sample size was not powered for confirmatory testing, only descriptive statistics will be provided.
 
Number of patients per trial approach group: randomization using a ratio 1 (virtual):1 (traditional).
 
Nevertheless, a precision calculation based on the 2-sided 95% confidence interval (CI) shows that the change in HbA1c from baseline in virtual approach, the change in HbA1c from baseline in traditional approach and the difference in HbA1c change between the two approaches will be estimated with a precision of approximately 0.37%, using a standard deviation (SD) of 1.1 and taking into account an up to 10% rate of non-evaluable patients for HbA1c.
 
General aspects of the analyses:
 
Except if defined below, the baseline value will be the last available value prior to the first injection of IMP.
 
Analysis population:
 
The primary population for all non-safety endpoints will be the Intent-To-Treat (ITT) population, which will comprise all randomized

[figure not shown]

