1.2 STUDY FLOW CHART

(☎ = virtual visits; 📞 = phone call visits; P = on-site in-person visits)

Visits	Screening		Randomization		Treatment period										Follow-up
	1 Step-1 ^a	1 Step-2 ^b	2 Step-1 ^c	2 Step-2 ^d	3	4	5	6	7	8	9	10	11	12 EOT ^g	13 EOS
Traditional group	☎ (Digital screening)		📞	P	📞	📞	📞	P	📞	P	📞	P	📞	P	📞
Virtual group	☎ (Digital screening)		📞	P & ☎	☎	☎	☎	☎	☎	☎	☎	☎	☎	☎	☎
Weeks	-3	-2	-1	0	1	2	3	4	6	8	12	16	20	24	1 week
Window (day)			-/+ 4		-/+ 3	-/+ 3	-/+ 3	-/+ 4	-/+ 3	-/+ 4	-/+ 3	-/+ 4	-/+ 3	-/+ 3	+/-2
Informed Consent (eConsent)	X														
Schedule Homecare visit	X														
Interactive response technology (IRT) calls	X		X				X		X		X		X		
Inclusion	X	X													
Exclusion		X													
Demography	X	X													
Video chat with Investigator and site staff	X	X													
Medical and surgical history; diabetes history		X													
Concomitant medication(s)		X		X	X	X	X	X	X	X	X	X	X	X	X
Physical examination ^d				X											
Vital signs ^h and body weight		X		X			X		X		X		X		
Height		X													
Virtual material/device shipment (Bluetooth devices) ^e			X												
Dispensation/collection of e-diary				X	X	X	X	X	X	X	X	X	X	X	

Visits	Screening		Randomization		Treatment period										Follow-up
	1 Step-1 ^a	1 Step-2 ^b	2 Step-1 ^c	2 Step-2 ^d	3	4	5	6	7	8	9	10	11	12 EOT ^g	13 EOS
Traditional group	Ⓢ (Digital screening)		☎	P	☎	☎	☎	P	☎	P	☎	P	☎	P	☎
Virtual group			☎	P & Ⓢ	Ⓢ	Ⓢ	Ⓢ	Ⓢ	Ⓢ	Ⓢ	Ⓢ	Ⓢ	Ⓢ	Ⓢ	Ⓢ
Weeks	-3	-2	-1	0	1	2	3	4	6	8	12	16	20	24	1 week
Window (day)			-/+ 4		-/+ 3	-/+ 3	-/+ 3	-/+ 4	-/+ 3	-/+ 4	-/+ 3	-/+ 4	-/+ 3	-/+ 3	+/-2
Randomization via IRT call			X												
Video chat with investigator and site staff via the virtual device ^e				X	X	X	X	X	X	X	X	X	X	X	X
Allocation of study medication (IMP)				X				X		X		X			
First IMP (Toujeo) injection ^e				X											
Documentation and review of IMP and NIMP doses ^f				X	X	X	X	X	X	X	X	X	X	X	
IMP compliance check; collecting & counting used & unused pens								X		X		X		X	
Diet and lifestyle counselling		X		X	X	X	X	X	X	X	X	X	X		
Glucose meter shipment ^c			X												
7-Point SMPG ⁱ				X								X		X	
5-point SMPG ⁱ				X	X	X	X	X	X	X	X	X	X	X	
Upload SMPG to PC ^j				X				X		X		X		X	
AE/SAE	To be assessed and reported (if any) since consent throughout the study (report SAE to the sponsor within 24 hours)														
Hypoglycemia recording	To be assessed and reported (if any) since randomization throughout the study														

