8.1.6 Adjustment of investigational medicinal product

Investigators should follow Toujeo prescribing information to adjust Toujeo (9) dose. It is expected that a higher dose of Toujeo is needed to maintain the same level of glycemic control, when patients shift the basal insulin from insulin glargine 100 U/mL (eg, Lantus or Basaglar) to Toujeo. During the treatment period, Toujeo will be titrated at the investigator's discretion to achieve the fasting glycemic target while avoiding hypoglycemia.

The target range for fasting (prebreakfast/preinjection) plasma glucose is between 80 and 130 mg/dL (4.4 and 7.2 mmol/L).

The upward dose titration should continue until the patient reaches the target fasting (prebreakfast/preinjection) SMPG. All efforts should be made to reach the target ranges for plasma glucose by 6 to 8 weeks post randomization. Thereafter, the dose will be adjusted as necessary to maintain the glycemic control until the end of treatment (EOT) at Week 24.

Changes in the Toujeo dose are based on the average fasting pre-breakfast SMPG values of past 3 days measured by the patients. If the fasting SMPG is ≥ 130 mg (7.2 mmol/L), the Toujeo dose will be increased by 10%. [Table 1](#) provides examples for the 10% titration rule. Other preprandial (prelunch, predinner) SMPG measurements may also be taken into account.

If considered helpful to achieve the fasting glycemic target by the investigator, the mealtime insulin (including bedtime) may be titrated before additional basal insulin titration to achieve a bedtime and prebreakfast glucose delta < 50 mg/dL.

A dose increase may be split into 1-2 incremental dose steps rather than implementing the entire dose increase at once, if it is considered by the investigators or medically qualified designee to be in the best interest of the patient to do so. The dose of Toujeo should be titrated no more frequently than every 3 to 4 days.

Table 1 – Titration of investigational medicinal product dose

Toujeo daily dose	10% increase rules
Up to 21 u	2 u , or split into 2 x 1 u over 3 days apart
22 to 29 u	2 or 3 u , split into 2 or 3 x 1 u over 3 days apart
30 to 36 u	3 u, split into 3 x 1 u over 3 days apart
37 to 44	3 or 4 u, split into 2 x 2 u over 3-4 days apart
≥45 u	4 u , split into 2 x 2 u over 3-4 days apart

Good clinical judgment is to be exercised while titrating the basal insulin dose.

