Patients will be instructed to measure finger stick plasma glucose levels prior to the administration of carbohydrates whenever symptomatic hypoglycemia is suspected, unless safety considerations necessitate immediate glucose rescue prior to confirmation, and then a glucose measurement should be performed as soon as safe, with appropriate diary documentation. Details on hypoglycemia episodes will be captured in the patient diaries, and patients will contact the sites as soon as possible following severe events to review the details and decide on any necessary measures to be taken.

- **Asymptomatic hypoglycemia**

Asymptomatic hypoglycemia is an event not accompanied by typical symptoms of hypoglycemia but with a measured plasma glucose concentration less than or equal to 70 mg/dL (3.9 mmol/L).

- **Probable symptomatic hypoglycemia**

Probable symptomatic hypoglycemia is an event during which symptoms typical of hypoglycemia are not accompanied by a plasma glucose determination, but was presumably caused by a plasma glucose concentration less than or equal to 70 mg/dL (3.9 mmol/L); symptoms treated with oral carbohydrate without a test of plasma glucose.

- **Relative hypoglycemia**

Relative hypoglycemia recently termed “pseudo-hypoglycemia” (19) is an event during which the person with diabetes reports any of the typical symptoms of hypoglycemia with a measured plasma glucose concentration >70 mg/dL (>3.9 mmol/L) but approaching that level.

- **Nocturnal hypoglycemia**

Nocturnal hypoglycemia is any hypoglycemia of the above categories that occurs:

- Between 00:00 and 05:59, regardless whether patient was awake or work up because of the event
- Sleep status: patient was asleep between bedtime and before getting up in the morning, ie, before the morning determination of fasting pre-breakfast SMPG and patient woke up due to the hypoglycemia

9.2.4.4.2 *Reporting hypoglycemia*

All hypoglycemia episodes will be documented on the dedicated hypoglycemia event page in the e-CRF. The information about the hypoglycemic events including onset date/time, counter-measurements, whether the patient needed assistance from other to treat the hypoglycemic event, etc. will be collected to support hypoglycemia analyses.

Hypoglycemic events and the symptoms accompanying the events will not be reported as an AE. However, symptomatic hypoglycemia events fulfilling the criteria of an SAE will be documented

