10.1.6 Follow-up Visit (Visit 13)

Following the last administration of IMP either as scheduled or prematurely, a post-treatment follow-up should be scheduled for all the patients in one week (+/- 2 days) after permanent discontinuation of the study treatment. This visit can be a virtual of phone call visit, or an on-site visit in case of ongoing or new AE during the post-treatment period, if needed. The patient is called by the investigator or qualified designee at scheduled time. If the call has not been performed by the investigator, the investigator has to be consulted if AE/SAE and hypoglycemic event are suspected.

During the phone call the same set of questions as listed for other telephone/virtual visits has to be asked ([Section 10.1.3](#)), except IMP-related questions.

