11.4.3.4 Analyses of safety endpoints

Safety endpoints are described in [Section 9.2.4](#).

The summary of safety results will be presented by approach group.

All safety analyses will be performed on the safety population, on the on-treatment period, defined as the time from first IMP injection up to 2 days after the last IMP injection.

The baseline value for safety endpoints will be the last available value prior to the first injection of IMP.

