2.1.4.1 Hypoglycemia events

All hypoglycemia will be categorized according to the ADA definitions (1) as described below:

- **Severe hypoglycemia:** Severe hypoglycemia will be derived as an event requiring assistance of another person to actively administer carbohydrate, glucagon, or other resuscitative actions.
- **Documented symptomatic hypoglycemia:** Documented symptomatic hypoglycemia will be derived as an event with symptoms of hypoglycemia and with a measured plasma glucose concentration less than or equal to 3.9 mmol/L (70 mg/dL).

- **Asymptomatic hypoglycemia:** Asymptomatic hypoglycemia will be derived as an event without symptoms of hypoglycemia but with a measured plasma glucose concentration less than or equal to 3.9 mmol/L (70 mg/dL).
- **Probable symptomatic hypoglycemia:** Probable symptomatic hypoglycemia will be derived as an event with symptoms of hypoglycemia and missing plasma glucose concentration.
- **Relative hypoglycemia:** Relative hypoglycemia (recently termed “pseudo-hypoglycemia”) will be derived as an event with symptoms of hypoglycemia but with a measured plasma glucose concentration greater than 3.9 mmol/L (70 mg/dL).

Hypoglycemia episodes will be analyzed regardless of the time of onset and in the following time periods defined by time of the day:

- Nocturnal hypoglycemia (defined by time of the day): any hypoglycemia that occurs between 00:00 and 05:59 a.m. hours, regardless whether patient was awake or woke up because of the event.
- Daytime hypoglycemia (defined by time of the day): any hypoglycemia that occurs between 6:00 a.m. to 23:59.
- Nocturnal hypoglycemia (defined by sleep status): any hypoglycemia waking the patient up from sleep after having gone to bed in the evening and before getting up in the morning (ie, before the morning determination of fasting pre-breakfast SMPG and before administration of insulin (IMP or NIMP)).

Some analyses will be also performed by distribution by hour of the day (0:00-23:59).

Hypoglycemia episodes will be analyzed only during the following period:

- 24-weeks TEAE period,

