2.4.5.1 Analyses of hypoglycemia

All analyses of hypoglycemia events will be performed on the safety population, separately on events occurring during the 24-Weeks TEAE period (as defined in [Section 2.1.4](#)). The analyses planned to be done during the 24-Weeks TEAE period only (as defined in [Section 2.1.4.1](#)).

Patients with at least one hypoglycemia event

- Number and incidence of patients with at least one hypoglycemia event will be presented for any hypoglycemia and for each hypoglycemia ADA category, overall and by time of the day (as described in [Section 2.1.4.1](#)).
- For any hypoglycemia and for each hypoglycemia ADA category (except probable, pseudo), incidence of patients with at least one hypoglycemia will be compared, overall and by time of the day. Odds Ratio and its corresponding 95% CI of Virtual group over Traditional group for each hypoglycemic event will be estimated by a logistic regression model adjusted on randomization strata of screening HbA1c (<7.6%, ≥7.6%) and randomization strata of sites.
- Percentage (%) of patients with at least one severe hypoglycemia event will be summarized by symptom during 24 weeks TEAE period,

Number and rate of hypoglycemia event

- Number and rate of hypoglycemia event per patient-year will be summarized for any hypoglycemia and for each hypoglycemia ADA category (as described in [Section 2.1.4.1](#)), overall and by time of the day (as described in [Section 2.1.4.1](#)). Non classified hypoglycemia will be displayed.
- For any hypoglycemia and for each hypoglycemia ADA category (except probable, pseudo), the number of hypoglycemia events per patient-year will be compared, overall and by time of the day. For each hypoglycemic event, the rate ratio, and its corresponding 95% CI, of Virtual group over Traditional group will be estimated using an over-dispersed Poisson regression model adjusted on randomization strata of screening HbA1c (<7.6%, ≥7.6%) and randomization strata of sites.

For Hypoglycemic ADA categories, only the threshold hypoglycemia episodes with plasma glucose ≤70 mg/dL (3.9 mmol/L) will be analyzed.

Subgroups analyses

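### Non-serious hypoglycemia recorded outside the window from first Toujeo dose to 2 days after the last has no planned table or listing

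*SAP*

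**What the plan says.** **Collection.** The flow chart (Protocol 1.2) gives the hypoglycemia recording period as "To be assessed and reported (if any) since randomization throughout the study". For the follow-up contact, Protocol 10.1.6 says "During the phone call the same set of questions as listed for other telephone/virtual visits has to be asked", leaving out only the questions about study drug. The questions it refers to (Protocol 10.1.3) include hypoglycemic events.

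**Analysis window.** SAP 2.1.4.1 says "Hypoglycemia episodes will be analyzed only during the following period" and lists the 24-week TEAE period. SAP 2.4.5.1 repeats the restriction: "The analyses planned to be done during the 24-Weeks TEAE period only (as defined in" the SAP's own definitions. SAP 2.1.4 ends that period 2 days after the last injection. Protocol 11.4.3.4 sets the same limit: "All safety analyses will be performed on the safety population, on the on-treatment period".

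**Separation from adverse events.** Protocol 9.2.4.4.2 says "Hypoglycemic events and the symptoms accompanying the events will not be reported as an AE", with an exception for events that meet the seriousness criteria. Protocol 9.2.4.4.1 makes a severe event, one needing another person's help, an SAE only if it meets those criteria. SAP 2.4.5.2 plans tables for pre-treatment and post-treatment adverse events and for post-treatment SAEs. It plans none for hypoglycemia.

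**Endpoint and reporting promise.** The Protocol synopsis words the endpoint as "Hypoglycemic events and incidence rate (as per the American Diabetes Association (ADA) classification) during the 24-week period in each group". Protocol 10.5 commits the sponsor to put all safety observations in the study report.

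**The concern.** Hypoglycemia is a central harm when insulin is titrated to glucose targets. The plan collects it over a longer span than it reports, and the route that catches other adverse events outside the treatment window is closed to it.

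The matter is most relevant for patients who stop Toujeo early. Toujeo is the same in both arms, and what is randomized is the virtual or traditional approach, which continues after Toujeo stops. HbA1c is kept to Week 24 regardless of discontinuation (SAP 2.1.3 and 2.1.3.1), while hypoglycemia in the same patients is cut 2 days after the last injection. In those patients glycemic control and its main harm would be described over different time spans.

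**Working it through.** The documents give no figure to reproduce, so the check has two parts: tracing one event, then sizing the gap.

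**Trace.** Take a treated patient with a non-serious hypoglycemic event starting on day 3 or later after the last injection.

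1. It is recorded: Protocol 1.2 and 10.1.6, on the dedicated hypoglycemia page (Protocol 9.2.4.4.2).
2. It is outside every hypoglycemia analysis: SAP 2.1.4.1 and 2.4.5.1, Protocol 11.4.3.4.
3. It is not in the post-treatment adverse event table, because it is not an adverse event, nor in the SAE tables or listing, because it is not serious.
4. The other listings in SAP 2.4.5.2 and 2.4.5.3 cover adverse events leading to discontinuation, events of special interest, and deaths. They would not show it unless it was also, for example, a symptomatic overdose.

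The same trace applies to an event between randomization and first dose.

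**Size.** Inputs:
- Visit 2-Step 2 at 7 ± 4 days after randomization (Protocol 8.1.5), taking the first dose on that day
- Visit 13 at 7 ± 2 days after the last dose (Protocol 10.1.6)
- Window end at last dose + 2 days (SAP 2.1.4)
- 24 weeks = 168 days
- 15 patients randomized (SAP 2)

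(a) Randomization to first dose: 7 days (3 to 11). With 15 patients, 15 × 7 = 105 days, and 105 / 365.25 = 0.29 patient-years (0.12 to 0.45).

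(b) Follow-up week: Visit 13 day − 2 = 7 − 2 = 5 days (3 to 7). If all 15 complete, 15 × 5 = 75 days, and 75 / 365.25 = 0.21 patient-years (0.12 to 0.29 across the visit window). The analysed time would be 15 × 170 / 365.25 = 6.98 patient-years, so the follow-up-week part is 75 / (2550 + 75) = 2.9% of the two combined.

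(c) Premature stop at week *w*, followed to Week 24: uncovered days = 168 − 7*w* − 2.

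| Stop at week | Uncovered days | Share of 168 days |
|---|---|---|
| 4 | 138 | 82% |
| 8 | 110 | 65% |
| 12 | 82 | 49% |
| 16 | 54 | 32% |
| 20 | 26 | 15% |

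These are per patient. The documents give no rate of Toujeo discontinuation, so no total for (c) can be derived. One patient stopping at Week 8 and followed to Week 24 contributes 110 / 365.25 = 0.30 patient-years, more than the nominal follow-up-week part for all 15.

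**The case against.** **The window is deliberate and consistent.** The synopsis, Protocol 9.2.4 and 11.4.3.4, and SAP 2.1.4, 2.1.4.1 and 2.4.5.1 agree on it. The synopsis endpoint refers to 24 weeks but does not say regardless of discontinuation. Event rates use patient-years of exposure (Protocol 11.4.3.4.1), so events and time are cut together. This stands: the on-treatment rate is coherent and should remain the main result. It does not explain why other adverse events get outputs outside the window and hypoglycemia gets none.

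**The events may still be reported.** A reader might infer that these events are reported nowhere. That goes too far. Protocol 10.5 promises all safety observations, and SAP 2 allows tables or listings after early termination. Neither names an output or changes the window, so the supportable statement is that none is planned.

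**The gravest events are covered.** Seizure, unconsciousness and coma must be reported as SAEs, and any serious event reaches the SAE outputs. Events with missing or partial onset dates count as emergent unless other information classifies them otherwise (SAP 2.5.3). Safety data from patients outside the safety population are listed separately (SAP 2.4.5). All of this stands and confines the gap to non-serious, dated events in treated patients.

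**Part (c) may be smaller than it looks.** Flow chart footnote g and Protocol 10.3.4 continue study procedures after a premature stop. Protocol 6.2.1 and 10.1.6 place the follow-up contact one week after it, and the Week 24 visit is only as far as possible. This stands. The passages need to be reconciled, and (c) applies only as far as patients are actually followed.

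**Two further inferences fail.** A reader might argue that the odds ratios and rate ratios are biased by conditioning on stopping Toujeo. With 15 patients randomized, SAP 2 abandons the planned analyses for basic descriptive statistics, so that argument carries little weight here. A reader might also link the follow-up week to a change of basal insulin, because Protocol 8.1.6 says "It is expected that a higher dose of Toujeo is needed to maintain the same level of glycemic control". That sentence concerns the switch to Toujeo, and Protocol 10.3.4 allows Toujeo to be prescribed after discontinuation. No change of insulin in that week is established.

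**Conclusion.** The point holds as a gap in planned reporting. No table or listing in either document would show non-serious hypoglycemia, including non-serious severe events, in a treated patient before the first dose or from day 3 after the last. The SAP thus leaves the promise in Protocol 10.5 without an output for these events.

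For patients who complete treatment the gap is small. For early discontinuers it can be most of the 24 weeks, but how many there are and how long they are followed is not in the documents. The patient-year figures assume that all 15 contribute at the stated visit timing. The documents do not support a claim of suppressed harm or of a biased comparison. This is a cheap improvement to completeness, and the on-treatment analysis is not at fault.

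**What to change.** Keep the TEAE-period analysis as the main one. In SAP 2.1.4.1 and 2.4.5.1, with a matching line in Protocol 11.4.3.4, add:

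1. A by-arm listing of all hypoglycemia outside the TEAE period (randomization to first dose, and day 3 after the last injection to end of study), by ADA category.
2. Descriptive by-arm counts, incidence and crude rates from first dose to Week 24 or last study contact, regardless of Toujeo discontinuation, with time in study as person-time.

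The second output starts at first dose, whereas the SAP's HbA1c period starts at randomization. The listing covers the days between.

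The cost is a few lines of text and two outputs from the existing hypoglycemia page, with no new data, visits or staff. The small downside is that events after a stop occur on mixed basal insulins, so they belong beside the on-treatment result and do not replace it.
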